3.2.1 Primary Objective Estimand

[Table 1](#) presents the estimand for the primary objective.

Table 1: Primary Objective Estimand

Objective	To evaluate the efficacy of rimegepant compared to placebo in providing symptomatic pain relief in patients with refractory TN, defined as a reduction from baseline in the average daily NPRS between the two-week treatment phases.
Efficacy Endpoint	Change from baseline to the average of the 2-week treatment phase of the study in the average daily NPRS
Summary	Using the modified Intent to Treat (mITT) population: 
• Descriptive statistics for the averaged daily NPRS score and change from baseline score as a continuous variable by treatment group at each 2-week treatment phase• Difference in mean change from baseline in average daily NPRS scores between treatment groups estimated using a mixed-effect model for repeated measures (MMRM)
Intercurrent Events	Study drug discontinuation: while-on-treatment strategy

3.2.2 Secondary Objective Estimands

Table 2 presents the estimands for secondary objectives.

Table 2: Secondary Objective Estimands

Objective 1	To assess the safety and tolerability of rimegepant relative to placebo in patients with TN
Safety Endpoint	Frequency of unique subjects with: SAEs, AEs leading to discontinuation, AEs judged to be related to study medication, S-STS total score, and clinically significant electrocardiogram (ECG) and laboratory abnormalities observed during the randomization phase of the study
Summary	Using the treated subjects population: 
Number and percentage of subjects with these events or findings
Intercurrent Events	Study drug discontinuation: while-on-treatment strategy for AEs; treatment policy strategy for all other safety endpoints
Objective 2	To evaluate the efficacy of rimegepant vs placebo for improving physical function in TN patients as measured by Penn-FPS-R
Efficacy Endpoint	Change in Penn-FPS-R total score from baseline to the end of the 2-week treatment phase of the study
Summary	Using the mITT population: 
Descriptive statistics for Penn-FPS-R and change from baseline as a continuous variable by treatment group at each visitDifference in mean change from baseline in Penn-FPS-R scores between treatment groups estimated using MMRM
Intercurrent Events	Study drug discontinuation: treatment policy strategy
Objective 3	To evaluate the efficacy of rimegepant vs placebo for improving functional disability in TN patients as measured by the Pain Disability Index
Efficacy Endpoint	Change in Pain Disability Index total score from baseline to the end of the 2-week treatment phase of the study
Summary	Using the mITT population: 
Descriptive statistics for Pain Disability Index and change from baseline as a continuous variable by treatment group at each visitDifference in mean change from baseline in Pain Disability Index between treatment groups estimated using MMRM
Intercurrent Events	Study drug discontinuation: treatment policy strategy
Objective 4	To evaluate the efficacy of rimegepant vs placebo on global functioning as measured by the PGI-C
Outcomes Research Endpoint	PGI-C Scale at the end of the 2-week treatment phase of the study
Summary	Using the mITT population: 
Descriptive statistics for PGI-C score as categorical variable by treatment group at each visitDifference in PGI-C score between treatment groups estimated using MMRM

Intercurrent Events	Study drug discontinuation: treatment policy strategy
Objective 5	To evaluate the efficacy of rimegepant vs placebo in providing symptomatic pain relief as captured by daily rating of worst pain episode as measured by the 11 point NPRS
Efficacy Endpoint	Change from baseline to the average worst pain NPRS scores in a day in the 2-week treatment phase of the study
Summary	Using the mITT population: 
Descriptive statistics for the average worst pain episode NPRS scores and change from baseline score as a continuous variable by treatment group for each 2-week treatment phaseDifference in mean change from baseline in the average worst pain episode NPRS scores between treatment groups estimated using MMRM
Intercurrent Events	Study drug discontinuation: while-on-treatment strategy
Objective 6	To evaluate the efficacy of rimegepant vs placebo in providing symptomatic pain relief of clinical importance as defined by a 2-point or greater reduction in the 11 point NPRS
Efficacy Endpoint	Percentages of subjects with ≥ 2 point reduction from baseline in average daily NPRS score
Summary	Using the mITT population: 
Number and percentages by treatment group and odds ratio between treatment groups using logistic regression
Intercurrent Events	Study drug discontinuation: while-on-treatment strategy

CCI

4 ANALYSIS SETS, TREATMENT GROUPS, AND SUBGROUPS

4.1 Analysis Sets

The following analysis sets will be evaluated and used for presentation and analysis of the data:

- Enrolled: Patients who signed an informed consent form and were assigned a Patient Identification number (PID).
- Full: Enrolled subjects who received a treatment assignment from the IWRS (rimegepant or placebo).
- Treated: Enrolled subjects who received at least 1 dose of study therapy (rimegepant or placebo).
 - DBT treated: Subjects in the treated analysis set who took ≥ 1 dose of DB study drug (rimegepant or placebo), i.e., nonmissing study drug start date.
 - Interim treated: Subjects in the treated analysis set with safety data entered during the interim period (post-DBT pre-OL period).
 - OL rimegepant treated: Subjects in the treated analysis set who took ≥ 1 dose of OL rimegepant, i.e., nonmissing OL rimegepant start date.
 - DB or OL rimegepant treated: Subjects in the treated analysis set who took ≥ 1 dose of DB or OL rimegepant, i.e., nonmissing DB or OL rimegepant start date.
 - Follow-up treated: subjects in the treated analysis set whose last contact date is in the follow-up period.
- Modified Intent to Treat (mITT): Randomized subjects who received at least 1 dose of study therapy and provided a baseline and at least one post-baseline efficacy assessment in each sequence.

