### **1.3.1     *Study Design Rationale***

This is a phase 2, multi-center, double-blind, placebo-controlled, crossover trial to assess the safety, tolerability, and efficacy of BHV-3000 in treating Trigeminal Neuralgia. The study drug/medication will be rimegepant formulated in a 75 mg immediate release (IR) tablet or a matching placebo. The subjects will be instructed to take their study drug/medication, as an outpatient, daily during two 2-week treatment sequences (separated by a 7-day placebo washout period).

Approximately 120 patients will be screened to randomize 60 patients in a 1:1 ratio into 2 treatment sequences receiving 75 mg Rimegepant vs Placebo, using a 2-period, 2-sequence, crossover design. Patients with atypical TN and typical TN will be stratified equally into each of the two treatment sequences, with atypical TN patients not exceeding 50 percent of the subjects.

In addition, subjects completing the double-blind phase of the study and who continue to meet eligibility criteria may be offered up to 12 weeks of Open-Label Extension treatment, provided the Principal Investigator (PI) believes open-label treatment offers an acceptable risk-benefit profile. Subjects who agree to enter the Open-Label Extension Phase will not be required to have a wash-out period of drug, but instead should continue dosing as specified in the Open-Label Extension Phase. During the Open-Label Extension phase, study drug/medication is rimegepant (BHV-3000) 75 mg orally disintegrating tablet (ODT) dosed daily.

All subjects will undergo a post study Follow-up Safety Visit 14 days after the final EOT Visit and last dose of study drug/medication administration. Subjects who discontinue from the study at any time during either the Double-Blind Phase or the Open-label Extension Phase are expected to complete the End of Treatment (day 119) Visit **and** the 2-Week Follow-up Safety Visit.

All randomized subjects should complete the 2-Week Follow-up Safety Visit (regardless of completing the Double-blind Treatment Phase), except those who are lost to follow-up, withdrew consent, or death.

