During each 2 week treatment phase and during the 7 day placebo washout period, patients will complete the 11 point NPRS daily, as described above. In addition, patients will complete a paper diary daily to record efficacy data. The diary will include the daily recording of overall pain using the 11 point NPRS, a recording of daily use of rescue medications, and a daily rating of worst pain episode using the 11 point NPRS. Other secondary endpoints will be assessed at the beginning and end of each treatment period, including the Penn Facial Pain Scale (a 12-item activities of daily living scale designed specifically to assess impact of TN symptoms on daily activities), the Pain Disability Index (which measures the degree to which chronic pain interferes with 7 categories of daily activities, measured on an 11 point scale ranging from 0 (no disability) to 10 (worst disability)). The Patient Global Impression of Change (PGI-C: a patient self-reported global index scale) will be assessed at the end of each treatment sequence. In addition, the Sheehan-Suicidality Tracking Scale (S-STS) will be administered as a safety measure at screening, as well as at every visit, as specified in the protocol.

In addition, subjects completing the DBT Phase of the study and who continue to meet inclusion/exclusion criteria may be offered up to 12 weeks of OLE treatment, provided the Principal Investigator (PI) believes open-label treatment offers an acceptable risk-benefit profile. Subjects who agree to enter the OLE Phase will not be required to have a wash-out period of drug, but instead should continue dosing as specified in the OLE Phase.

All subjects will undergo a post study Follow-up Safety Visit 14 days after the final EOT Visit and last dose of study drug/medication administration. Subjects who discontinue from the study at any time during either the DBT Phase or the OLE Phase are expected to complete the End of Treatment (day 119) Visit and the 2-Week Follow-up Safety Visit.

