6.2.3.1 Subject Disposition during the DBT Phase

Subject disposition during the DBT phase will be summarized for treated subjects by as-treated treatment sequence and overall as the number and percentage of subjects in the following categories:

- Completed the first treatment period
- Withdrawn from the first treatment period
 - Reasons for withdrawal, including not reported
- Completed the second treatment period
- Withdrawn from the second treatment period
 - Reasons for withdrawal, including not reported.
- Continuing to the OLE phase
- Not continuing to the OLE phase

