6.3 Efficacy

Unless otherwise noted, the primary and secondary efficacy analyses will be conducted on the mITT population. DBT and OLE efficacy data will be included in listings by subject, treatment sequence and period, study phase and visit (as applicable). Descriptive summary statistics will be provided for DBT and OLE phase data. Statistical analyses outlined in Table 3: Primary and Secondary Efficacy Estimands and Analyses will only be done for the DBT phase data.

Table 3: Primary and Secondary Efficacy Estimands and Analyses

Index	Description	Variable Type	Statistical Model	On-Study Data
Primary Estimand				
P01	Difference between treatment groups in change from baseline in average daily NPRS scores at the end of the randomization phase	Continuous	MMRM	Baseline, Day 14, 21, 35
Secondary Estimand				
S01	Difference between treatment groups in change from baseline in Penn-FPS-R score at the end of the randomization phase	Continuous	MMRM	Baseline, Day 14, 21, 35
S02	Difference between treatment groups in change from baseline in Pain Disability Index at the end of the randomization phase	Continuous	MMRM	Baseline, Day 14, 21, 35
S03	Difference between treatment groups in PGI-C at the end of the randomization phase	Continuous	MMRM	Day 14, 21, 35
S04	Difference between treatment groups in change from baseline in worst pain episode measured by NPRS at the end of the randomization phase	Continuous	MMRM	Baseline, Day 14, 21, 35
S05	Difference between treatment groups in percentages of subjects with ≥ 2 point reduction from baseline in average daily NPRS score	Binary	Logistic Regression	Baseline, Day 14, 21, 35

MMRM = Mixed effects model for repeated measures

6.3.1 *Continuous Efficacy Endpoints*

Assessments are taken directly from reported CRF visits, aside from the NPRS endpoints which are only taken between treatment exposure start and end dates.

Descriptive Analyses

Summary statistics for parameter values are tabulated at select time points by treatment group (rimegepant pooled or placebo pooled).

MMRM

Treatment groups are assessed using MMRM with the following variables:

- Dependent variable: change from baseline of NPRS score averaged over each DBT period
- Fixed effects (categorical variables): treatment group, sequence, and period
- Covariate (continuous variable): baseline value of dependent variable

Random effect: subject error degrees of freedom are determined by the Kenward-Roger method.

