6.3.5.3 S03: Patient Global Impression of Change Scale (PGI-C)

The PGI-C is a patient-rated scale which assesses how the subject's current illness state has improved or worsened relative to the baseline visit. The subject is asked to rate a change in their overall disease condition on a 7-point scale, from 1 ('no change') to 7 ('a great deal better'). The PGI-C is a global index scale that may be used to rate the response of a condition to a therapy.

The PGI-C will be conducted at the beginning and end of each treatment phase as indicated in the Schedule of Assessments.

The PGI-C will be analyzed using the method specified in Section 6.3.2. The MMRM table has the same format as the one described in Section 6.3.2.

6.3.5.4 *S04: Worst Pain Episode*

Using the 11-point NPRS described above, subjects are asked to record an intensity rating of their worst pain episode over a 24-hour period daily in their paper diary.

Worst pain episode score will be analyzed using the same methodology as the primary endpoint (see Section 6.3.4.1) with baseline score as covariate.

6.3.5.5 *S05: ≥ 2 -Point Reduction in the 11 Point NPRS*

Achievement of ≥ 2 -point reduction in average NPRS score will be analyzed using logistic regression, that will include terms for treatment group, randomization strata (typical/atypical), sequence, and baseline NPRS score. See Section 6.3.3 for details. The regression table has the same format as the one described in Section 6.3.3.

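### The mITT rule, best read as an efficacy assessment in each period, drops patients with no period-2 assessment and discards period-1 data the planned mixed models could use; the number is unknown and the expected effect modest

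*SAP*

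**What the plan says.** SAP 4.1 defines mITT as randomised patients who took at least one dose and "provided a baseline and at least one post-baseline efficacy assessment in each sequence". Protocol 9.3 uses the same condition. SAP 6.3 states that, unless otherwise noted, "the primary and secondary efficacy analyses will be conducted on the mITT population".

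The word *sequence* is used in two ways. SAP 2.1 randomises each patient to one of two sequences, each containing both treatment phases and the washout. Protocol 1.3.1, however, has the patient dosing "daily during two 2-week treatment sequences (separated by a 7-day placebo washout period"). SAP 2.1 also says that PGI-C "will be assessed at the end of each treatment sequence", while SAP 6.3.5.3 says "The PGI-C will be conducted at the beginning and end of each treatment phase".

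For NPRS the estimand table gives "Study drug discontinuation: while-on-treatment strategy". For Penn-FPS-R, the Pain Disability Index (PDI) and PGI-C it gives "Study drug discontinuation: treatment policy strategy". The mixed models in SAP 6.3.1 and 6.3.2 have fixed terms for treatment, sequence and period and a random subject effect. SAP 6.1.3 relies on observed data without imputation. The disposition table in SAP 6.2.3.1 has a row for patients "Withdrawn from the first treatment period".

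SAP 7.2 takes period 2 from the Day 35 or Day 35/ET visit. For NPRS it derives the visits from exposure start and end dates.

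**The concern.** The set that carries every primary and secondary efficacy analysis is defined by a condition that no patient can meet as written, so two programmers could build different sets from it.

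Read as each period, the rule makes inclusion depend on a post-randomisation event. A patient who stops before any period-2 assessment is removed, and so are that patient's period-1 on-treatment NPRS diary scores and any Day 14 Penn-FPS-R, PDI and PGI-C scores. This fits poorly with the SAP's own strategies. Under while-on-treatment, a period-1 leaver already has usable NPRS scores. Under treatment policy, discontinuation is not supposed to matter.

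At stake are the least-squares mean difference and its 95% CI. They would describe only patients who reached a period-2 assessment, with some precision given away.

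**Working it through.** **1. Which reading.** Three readings are possible.
- Literal (an assessment in both sequences): no patient qualifies.
- The assigned sequence: one post-baseline assessment anywhere is enough, so nobody with period-1 data is excluded.
- Each period: both periods are needed.

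Protocol 1.3.1 and the PGI-C sentence in SAP 2.1 use *sequence* for a 2-week period within one patient. The phrase *in each* also makes sense only if a patient has more than one. The third reading is therefore the best supported.

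**2. Stated power.** Inputs from SAP 5 and Protocol 9.2: 60 randomised, 20% dropout, SD of the paired difference 3.8, difference 2, two-sided 0.05.
- Pairs: 60 × 0.8 = 48.
- Noncentrality: (2/3.8) × √48 = 3.65 on 47 df, so power is 94.6% (98.0% with 60 pairs).

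The stated figure of more than 90% reproduces. It already counts dropouts as lost pairs, so the mITT rule does not reduce it.

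**3. How many patients.** At the planned dropout the upper limit is 60 × 0.2 = 12, if every dropout precedes any period-2 assessment. The lower limit is 0. The documents do not split dropout by period.

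**4. Precision.** With r = 0.2 (SAP 5), the per-period variance is s² = 3.8²/(2 × 0.8) = 9.025, so s = 3.00. Assume all 20% leave with period 1 only, unrelated to score: n = 30 per sequence, nc = 24 with both periods. The variance V of the period difference in one sequence is:
- Both periods: 2s²(1−r)/nc = 2 × 9.025 × 0.8/24 = 0.602.
- All periods: s²[(1−r)²/n + (1−r²)/nc] = 9.025 × (0.64/30 + 0.96/24) = 0.554.

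The SE of the treatment difference is ½√(2V), giving 0.549 and 0.526. All-periods is 4.1% smaller, and the 48 pairs become worth about 52. At 5%, 10% and 30% loss the gain is 1.0%, 2.0% and 6.2%. At 20% loss with r = 0.5 or 0.7 it is 2.5% or 1.5%. The percentage does not depend on N.

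**5. Bias.** Assumptions not in the documents: true difference −2, no carryover or period effect, and logistic dropout before any period-2 assessment, with higher pain raising the odds. 20,000 simulated trials of 60 patients per scenario, 20% overall dropout, s = 3.0, r = 0.2.

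| Log-odds of dropout per SD | Observed-driven: both periods | Observed-driven: all periods | Unseen-driven: both periods | Unseen-driven: all periods |
|---|---|---|---|---|
| 0.5 | −1.97 | −2.00 | −1.97 | −1.96 |
| 1.0 | −1.91 | −2.00 | −1.91 | −1.89 |
| 1.5 | −1.85 | −2.00 | −1.85 | −1.82 |
| 1.0, plus 1.5 after rimegepant | −2.11 | −2.00 | −1.74 | −1.69 |

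*Observed-driven* means dropout follows the recorded period-1 score; *unseen-driven* means it follows the missing period-2 score. Dropout unrelated to score gives −2.00. In the observed-driven case the largest bias is 0.10 at 10% dropout and 0.06 at 5%; at 20% with r = 0.5 it is 0.09. A steeper slope of 2 at 20% dropout gives −1.81. If only patients given rimegepant first drop out, 20% to 40% of them and related to response, the both-periods estimate runs from −2.09 to −2.59 (r = 0.2 or 0.5).

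**6. Smaller trial.** SAP 1 reports early termination for low enrolment and gives no N. For illustration, with 20% loss the both-periods SE is 0.549, 0.776 and 0.950 at 60, 30 and 20 randomised. A bias of 0.15 is then 0.27, 0.19 and 0.16 of an SE.

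**7. Early-termination records.** Discontinuers are expected at an End of Treatment visit (Protocol 3.4 and Table 1 footnote i). For Penn-FPS-R, PDI and PGI-C, SAP 7.2 sets no condition on when the patient stopped, so a period-1 leaver's ET score could be filed as period 2. NPRS is bounded by exposure dates and does not share this doubt. But the mITT rule is not endpoint-specific, so an ET questionnaire filed as period 2 could admit the patient and thereby keep the period-1 NPRS.

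**The case against.** The strongest reply is that exclusion is inferred. The SAP's analysis sections keep sequence and period apart, and if the rule means the assigned sequence, nobody with period-1 data is lost. That stands as a limit: the wording defect is certain, the exclusion is the likelier reading.

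A both-periods set also suits a design in which each patient is their own control, and it matches the paired, no-imputation sizing. SAP 6.2.1 lists exclusion reasons by patient. These points make the choice understandable, but they do not explain discarding observed data that the chosen model accepts.

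Other replies that stand:
- A patient who leaves before Day 14 may have no period-1 questionnaire to lose, so the loss is chiefly NPRS diary data.
- A single period-2 assessment may be enough to qualify, so 12 is a ceiling.
- The responder endpoint S05 uses a logistic regression with no subject term, so the mixed-model argument does not carry over to it.
- The Core SAP and mock tables were not available and might contain a wider-set analysis. However, this SAP is not silent on mITT and takes precedence where the two differ.

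A reader might infer that the primary result will be materially biased, or that using all periods cures the bias. The documents give no dropout mechanism that supports the first. The unseen-driven scenarios contradict the second.

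**Conclusion.** The point holds in limited form. The mITT condition is defective as written. On its best-supported reading it removes patients with no period-2 assessment along with period-1 data that the SAP's mixed models and estimand strategies would retain.

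The count cannot be determined: 0 to about 12 at the planned size, and unknown after early termination. The expected effect is modest under the assumptions shown: about 4% on the SE at 20% loss and r = 0.2, and roughly 0.03 to 0.15 points of bias when dropout follows the observed score. It is zero if dropout is unrelated to score, and larger only with a steeper dependence or strongly one-sided dropout.

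It would be wrong to infer lost power or a changed test result. The sizing already assumes 48 pairs, and SAP 5 states that significance will not be evaluated. The correction is worth making because it fixes the main efficacy population at little cost. Confidence is medium, since the reading is inferred.

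**What to change.** - **SAP 4.1:** replace the each-sequence condition with at least one post-baseline efficacy assessment in at least one treatment period. Fit all available periods in the SAP 6.3.1 and 6.3.2 mixed models and keep the both-periods set as a sensitivity analysis.
- **Protocol 9.3:** record the change as a departure. Make it before the double-blind data are unblinded, or label it as added afterwards.
- **SAP 7.2:** assign an ET record to the treatment period in which the patient last took study drug, so that a period-1 leaver's ET score counts as period 1 and is not lost. Say also how a record from someone who stops during the placebo washout is handled.
- **S05:** report the logistic regression on both sets.

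The cost is a few reworded sentences and one extra sensitivity table, with no new data. The downside is that the all-periods analysis gives no protection when dropout depends on unseen scores, and may then be slightly more biased than the both-periods set.
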